11.3.3. Mini Mental State Examination (MMSE)

The Mini Mental State Examination (MMSE) is a brief, standardized tool to grade subjects' neurocognitive function. It is an 11-question measure that tests five areas of neurocognitive function: orientation, registration, attention and calculation, recall, and language. The maximum score is 30 which corresponds to the best neurocognitive function. Following Brown et al. (Brown PD, 2003), the subject's neurocognitive function will be considered 'impaired' if the MMSE score is 26 or less and 'normal' if it is 27 or more. Since its creation in 1975 by Folstein et al. (Folstein MF, 1975), the MMSE has been validated and extensively used in both clinical practice and research. Following Tangalos et al. (Tagalos EG, 1996) and as previously used by Brown et al., a decline of more than 3 points in the MMSE score will be considered to represent clinically significant deterioration. In this study, MMSE will be collected up to progression.

The evolution of MMSE over time will be interpreted at 2-sided significance level $\alpha=0.05$ for exploratory purpose taking into account the attrition as a result of subjects assessed only until progression. All MMSE results will thus be conditional on the subjects being otherwise free of progression. The distribution of the MMSE at each time point of evaluation will be described on the two treatment arms separately using means and their associated standard error (a graphical display will be considered). Median and range will also be provided. The proportion of subjects with 'normal' and 'impaired' MMSE score at baseline and at key timepoints of evaluation (e.g., baseline, at end of radiation therapy and then every 16 weeks) will also be displayed.

Linear mixed models with treatment, a (linear) time effect, a time-treatment interaction as fixed effects and subject specific random effect is fitted. The covariance structure which minimizes Akaike Information Criteria (AIC) will be used.

Longitudinal plots of mean MMSE score and 95% confidence interval based on Least Square Means from the linear mixed model will be presented over all assessment times by treatment group.

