Younger age, better performance status and extent of resection have repeatedly been shown to be positive prognostic factors in glioblastoma patients. Furthermore, data from the EORTC 26981/22981-NCIC CE3 trial indicate that a Mini-Mental State Examination (MMSE) score of 27 or higher is associated with better outcome (Ref. 19). The majority of glioblastomas does not harbor molecular factors associated with a better prognosis in gliomas such as IDH mutation or 1p/19q co-deletion (Ref. 50). The DNA repair protein O-methylguanine-DNA methyltransferase (MGMT) removes the alkylation at the O-position of guanine induced by alkylating agents. Thereby, MGMT confers resistance to alkylating chemotherapeutic drugs such as nitrosoureas or temozolomide. MGMT is expressed if the gene promoter is unmethylated. In contrary, a methylated MGMT promoter leads to gene silencing and is associated with sensitivity to alkylating agents (Ref. 23). In glioblastoma patients who are treated with alkylating drug chemotherapy, MGMT promoter methylation is associated with prolonged progression-free and overall survival (Ref. 42; Ref. 29; Ref. 54).

Biopsy or surgical resection is mandatory to allow for a histopathological characterization of the tumor tissue. The emergence of various molecular markers stresses the importance of having sufficient amount of tissue in order to be able to perform all desired analyses. Results obtained in various retrospective analyses stress the hypothesis that gross total resection results in prolonged survival in glioblastoma patients (Ref. 7). Furthermore, data from prospective trials which took advantage of the fluorescent dye, 5-aminolevulinic acid (5-ALA), or intraoperative MRI in order to improve the extent of resection, showed that patients with more complete resections of malignant gliomas had an improved progression free survival (Ref. 40, Ref. 39).

Radiotherapy has been a standard treatment for patients with newly diagnosed glioblastoma for decades. Data from a prospective trial comparing best supportive care alone with best supportive care and additional

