9.1. Demographics and Baseline Characteristics

Demographic characteristics will be summarized using the following information from the Screening/Baseline Visit eCRF pages.

There will be no statistical comparison of demographic and baseline measurements between treatment arms.

At a minimum, the following continuous demographics and baseline characteristics will be summarized

- Age expressed in years (age = year of randomization – year of birth);
- Height expressed in cm;
- Weight expressed in kg; Body Mass Index (BMI) expressed in kg/m^2 (calculated via $\text{weight} / [\text{height}^2]$ where weight is expressed in kg and height in m); (BMI less than 19; BMI of 19 to less than 21; BMI of 21 to less than 23; BMI of 23 or greater);
- Body surface area (BSA), expressed in m^2 (set to BSA captured in the eCRF, otherwise calculated based on Dubois' methods, ie, $0.007184 * \text{height}^{0.725} * \text{weight}^{0.42}$, where height is expressed in cm and weight in kg if BSA missing in the eCRF);
- Clearance, calculated based on the Cockcroft Gault formula, where creatinine clearance (CrCl) (mL/min) = $(140 - \text{age}) (\text{weight} [\text{kg}] / 72 (\text{serum creatinine} [\text{mg}/\text{dL}]))$; for females, the formula is multiplied by 0.85) (Cockcroft, 1976);
- Relevant vital signs, i.e. systolic blood pressure, diastolic blood pressure and pulse rate;
- Mini mental state examination (MMSE) total raw score;

At a minimum, the following categorical demographics and baseline characteristics will be summarized:

- Age categories expressed in years (≤ 55 , >55) and (≤ 65 , >65);
- Sex (Female, Male);
- Ethnicity (Hispanic or Latino, Not Hispanic or Latino, Not reported);
- Race (American Indian or Alaska native, Asian, Black or African American, Native Hawaiian or Other Pacific Islander, White, Multiple, Other, Not reported);
- Baseline Eastern Cooperative Oncology Group (ECOG) Karnofsky Performance Status (70/80, 90/100);
- Electrocardiogram (ECG): Normal, Abnormal Not Clinically Significant, Abnormal Clinically Significant or Missing).
- Mini mental state examination (MMSE) total raw score (≤ 27 , >27);
- Baseline steroid use (yes, no),
- Hematology & Biochemistry values,
- Adverse Events (Common Terminology Criteria for Adverse Events [CTCAE] grade) before start of treatment;

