intervals (calculated by Greenwood formula's estimation of the standard deviation for rates and by Brookmeyer and Crowley technique for the median).

Unstratified Cox's proportional hazards model will be fitted for each subgroup defined in section 11.5 in the ITT population only. Forest Plot will be displayed with a subgroup by treatment interaction test.

All secondary analyses will be performed at 2-sided significance level $\alpha=0.05$ for exploratory purpose.

The originally planned re-randomization test will not be performed as further to the review by the IDMC, there was no evidence that marizomib provides a benefit in overall survival and by consequence no significant result had to be validated with a re-randomization test.

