11.3.1. Progression-free Survival

Progression-free survival will be defined as the number of days from date of randomization to the date of earliest disease progression based on Response Assessment in Neuro-Oncology (RANO) criteria (as determined by the Investigator) or to the date of death due to any cause, if disease progression did not occur (the date of progression or death or censoring - date of randomization + 1). Subjects for whom neither death nor progression have been documented will be censored at the date of the last radiological assessment that the subject was progression-free. If a subject has no post-baseline radiological assessment, then the data will be censored at the date of randomization.

Subjects with two or more missing assessments prior to a visit with documented disease progression (or death) will be censored at the last assessment where the subject was documented to be progression free. Subjects who received new anti-cancer therapy or cancer-related surgery prior to progression or death will not be censored at the last assessment where the patient was documented as progression free prior to the new anti-cancer therapy or cancer-related surgery. Censoring rules are documented in section 15.2.

The following PFS analyses will be performed at 2-sided significance level $\alpha=0.05$ for exploratory purpose. The stratified LogRank test will be applied on the PFS time to test for differences between the 2 treatment groups. The Cox's proportional hazards model stratified by the stratification factors assessed at randomization (except institution) will provide the HR (including 95% CI). Summary of associated statistics for each treatment arm (median PFS time, 6-, 12-, 18-, 24-month PFS rate estimates and estimates for every 6 months thereafter as applicable) will be displayed with 95% CI computed using the same methods as for OS, and the Kaplan-Meier curve for PFS will be presented.

Progression-free survival Kaplan-Meier estimates will be calculated and unstratified Cox's proportional hazards model will be fitted for each subgroup defined in Section 11.5 in the ITT population only. Forest Plot will be displayed with a subgroup by treatment interaction test.

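### The SAP splits MMSE at ≤27 versus >27 for the baseline table and the OS/PFS subgroups, while both documents set the impaired/normal boundary between 26 and 27

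*SAP*

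**What the plan says.** Three places agree on where the MMSE boundary lies.

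- SAP 11.3.3 classes neurocognitive function as impaired "if the MMSE score is 26 or less" and as normal from 27 upwards. Protocol 7.1.5 gives the same rule.
- SAP 11.3.3 also reports the proportions with "normal' and 'impaired' MMSE score at baseline and at key timepoints of evaluation", so this rule is applied to the baseline score as well as to later ones.
- Protocol section 1 cites earlier trial data in which an MMSE "score of 27 or higher is associated with better outcome".

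Two places use another boundary.

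- SAP 9.1 lists, among the categorical baseline characteristics, "Mini mental state examination (MMSE) total raw score (≤ 27 , >27").
- SAP 11.5 lists MMSE with the same ≤27 / >27 split among the OS and PFS subgroups.

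The SAP 11.5 groups go straight into reported results. For OS, SAP 11.2 says an unstratified Cox "model will be fitted for each subgroup defined in section 11.5 in the ITT population only". For PFS, SAP 11.3.1 says the "model will be fitted for each subgroup defined in Section 11.5 in the ITT population only". Both add a forest plot with a subgroup-by-treatment interaction test. SAP section 3 puts sections 9 and 11 in full into both the primary and the long-term follow-up reports.

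**The concern.** The documents define only one classification of MMSE, and the subgroup split does not follow it. A reader of the forest plot will naturally take the lower MMSE row as the cognitively impaired patients and the upper row as the normal ones, because that is how SAP 11.3.3 describes them elsewhere in the same report. As written, the lower row also contains patients whom the same SAP calls normal. The row's hazard ratio and the interaction test then refer neither to the defined impairment status nor to the prognostic cut cited in the protocol's background.

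The baseline reporting has the same problem. The ≤27 count under SAP 9.1 and the impaired count at baseline under SAP 11.3.3 will differ with no explanation.

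Baseline cognition matters for interpretation in this trial: the IDMC observed severe neurological and neuropsychiatric disorders with marizomib, and hallucination/delirium is an adverse event category of special interest (SAP 12.1.3).

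**Working it through.** The plan states no numerical result to reproduce here, so the check is to compare the two rules score by score and then to size the group affected.

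**Step 1. Possible scores.** SAP 11.3.3 states: "The maximum score is 30 which corresponds to the best neurocognitive function". Protocol Appendix I awards one point per correct response, so scores are whole numbers from 0 to 30.

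**Step 2. Apply both rules to every score.**

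| MMSE | Definition (Protocol 7.1.5, SAP 11.3.3) | SAP 9.1 and 11.5 | Same side? |
|---|---|---|---|
| 0–26 | impaired (≤26) | lower (≤27) | yes |
| 27 | normal (≥27) | lower (≤27) | **no** |
| 28–30 | normal (≥27) | upper (>27) | yes |

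The rules disagree at 27 and nowhere else. With a split of ≤26 versus ≥27, no score from 0 to 30 is classed differently from the definition.

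**Step 3. Effect on the baseline counts.** If both outputs use the same baseline score, then

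count(≤27) − count(≤26) = number scoring exactly 27.

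The two figures disagree unless nobody scores 27.

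**Step 4. Size.** Neither document gives the share scoring 27. Take 5–15% as an assumption. SAP section 2 gives 616 patients randomized at the 28 April 2020 cut-off, which is kept for the primary analysis, and 749 in total, all followed for the long-term analysis.

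- Primary analysis: 0.05 × 616 = 30.8, about 31; 0.15 × 616 = 92.4, about 92.
- Long-term follow-up: 0.05 × 749 = 37.45, about 37; 0.15 × 749 = 112.35, about 112.

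Missing baseline MMSE scores would lower these numbers.

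**Step 5. Is a second cut explained anywhere?** The subgroup list in Protocol 8.2.1 does not include MMSE, so the SAP added this subgroup without a protocol cut to follow. The main changes listed for SAP v2.0 do not mention it. No reason for ≤27 / >27 was found.

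**The case against.** The best defence is that SAP 9.1 and 11.5 do not label their groups impaired or normal and do not refer to 11.3.3. No sentence requires the subgroup cut to equal the impairment cut. The same split appears in both places, so a deliberate separate choice cannot be excluded. This much stands: the documents show two unreconciled boundaries. They do not prove a typing slip.

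Two stronger readings should be resisted.

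- A reader might infer that patients scoring 27 are misclassified outright. The text supports only that their placement conflicts with the one classification the documents define.
- A reader might infer that the lower subgroup's hazard ratio is biased, or diluted by better-prognosis patients. The documents do not support this. A hazard ratio among patients with MMSE ≤27 is still a valid comparison of randomized arms in a group defined at baseline. The background statement concerns all patients at 27 or above, not those at 27 compared with 26. A prognostic difference does not in itself distort a treatment effect or an interaction test.

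The consequences are also limited. SAP 9.1 makes no between-arm comparison, and it summarizes the raw score as a continuous variable too. SAP 11.2 describes the secondary analyses as exploratory, and SAP 11.4 bars efficacy conclusions from exploratory subgroup results. MMSE is not a stratification factor.

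None of this accounts for the difference between sections of the same SAP, and the defence offers no reason for the second cut.

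**Conclusion.** The inconsistency is real and confined to one score. Patients scoring 27 are normal in the MMSE endpoint analysis, yet they fall in the lower group with the impaired patients in the baseline table and in the exploratory OS and PFS subgroup analyses. Those subgroups do not represent impairment status as the documents define it, and the baseline counts will not reconcile.

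The size depends wholly on the assumed 5–15% share: about 31–92 of 616 in the primary analysis and 37–112 of 749 in the long-term follow-up. That the conflict exists does not depend on that assumption.

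The primary OS test, the alpha split, the power and the MMSE endpoint analysis itself, which uses the 26/27 boundary, are unaffected. The point is worth correcting because the mismatch would appear in reported results and is cheap to remove, not because it threatens the trial's main conclusion.

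**What to change.** Amend SAP 9.1 and SAP 11.5 to read MMSE ≤26 versus ≥27, matching SAP 11.3.3 and Protocol 7.1.5. State in 11.5 that the baseline score is meant, since its MMSE line does not say so.

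SAP v2.0 is described as signed before the database lock, so the change needs a dated, documented amendment rather than a silent edit. If outputs on the ≤27 / >27 split already exist, keep them as a supplementary presentation under that label. If that split was intended, the amendment should give the reason and say that its groups are not the impaired/normal groups.

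The cost is two SAP lines, one recode, the amendment record, and a rerun of the MMSE row of the baseline table and the MMSE entries of the OS and PFS subgroup analyses where these have been produced. No new data are needed.

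### The straight-line MMSE model understates an early drop at end of radiotherapy and creates a false baseline difference; whether its slope favours marizomib depends on how far the drop recovers

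*SAP*

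**What the plan says.** SAP 11.3.3 gives the model as "Linear mixed models with treatment, a (linear) time effect, a time-treatment interaction as fixed effects and subject specific random effect is fitted". For the covariance it says: "The covariance structure which minimizes Akaike Information Criteria (AIC) will be used". The model output is a plot of mean scores with 95% intervals, "based on Least Square Means from the linear mixed model will be presented over all assessment times by treatment group". The key assessment times are "baseline, at end of radiation therapy and then every 16 weeks", and follow-up is limited: "In this study, MMSE will be collected up to progression".

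The same section also plans summaries that do not use the model:
- "The distribution of the MMSE at each time point of evaluation will be described on the two treatment arms separately using means", with standard errors, median and range.
- "The proportion of subjects with 'normal' and 'impaired' MMSE score at baseline and at key timepoints of evaluation", again by visit.

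On status it says "The evolution of MMSE over time will be interpreted at 2-sided significance level" of 0.05, for exploratory purposes. Protocol 8.2.3.1 leaves a longitudinal analysis optional and defers its detail to the SAP.

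The SAP does not say which model quantity will be interpreted (treatment term, slope difference or a contrast at a visit). It does not say whether the random effect is an intercept, a slope or both. It gives no check of linearity and no alternative form for time.

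**The concern.** With one linear time effect, the least-squares means at all visits lie on one line per arm by construction. Choosing the covariance by AIC does not relax this, because it leaves the mean untouched. Only one post-baseline visit, at end of radiotherapy, falls in the chemoradiation period, and a single early point off the line is what this model shows least well. The free treatment term can also absorb part of a post-baseline deficit as a difference at time zero, where randomisation makes the expected difference nil.

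The stake is the reading of cognitive harm. The SAP introduction reports that the IDMC saw severe neurological and neuropsychiatric disorders with marizomib. MMSE is the performance-based cognitive test done at all centres; the fuller battery runs only at participating centres (Protocol 6.1 and 6.2). The mixed model is the only between-arm comparison of MMSE that the SAP specifies.

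**Working it through.** There is no figure in the plan to reproduce: neither document gives an MMSE effect size, SD or power. The check asks what the model returns, on average, for assumed true differences.

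**Inputs**
- From the documents: the model form; the visit pattern; 1:1 allocation; 749 randomised, so about 374 per arm.
- Assumed: visits at weeks 0, 7, 27, 43, 59, 75 and 91 (start about one week after randomisation, 6 weeks of radiotherapy, a 4-week break, then every 16 weeks); baseline MMSE included as a response; a true marizomib-minus-control difference of -2 at end of radiotherapy; SD 3; intraclass correlation 0.4 to 0.7; median time to progression 26 to 35 weeks, or no attrition; dropout equal in both arms and unrelated to MMSE.

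**Case without attrition, by hand.** With complete, balanced visits and a random intercept, the expected arm-difference line is the ordinary least-squares line through the true differences.

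Mean visit time T = 302/7 = 43.14 weeks; Sxx = 6,984.9; t1 = 7; drop D = 2; f = the fraction of the drop that persists at every later visit.

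Slope per week = D[(T - t1) - f(2T - t1)]/Sxx. Intercept = mean difference - slope x T.

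- Full recovery by the next visit (f = 0): slope = 2 x 36.14/6,984.9 = 0.01035 per week, x 52 = **+0.54 per year**. Intercept = -2/7 - 0.01035 x 43.14 = **-0.73** (truth 0). Fitted at week 7 = -0.73 + 7 x 0.01035 = **-0.66** (truth -2.0).
- Full persistence (f = 1): slope = -2 x 43.14/6,984.9 = -0.01235 per week = **-0.64 per year**. Intercept = -12/7 + 0.01235 x 43.14 = **-1.18**. Fitted at week 7 = **-1.27**.
- The slope changes sign at f = 36.14/79.29 = **0.46**.

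**With attrition and correlation** (expected generalised least-squares estimates, random intercept, including the case above):

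| True course after -2.0 at end of radiotherapy | Fitted at end of radiotherapy | Slope difference, points/year |
|---|---|---|
| Full recovery by next visit | about -0.65 to -0.71 | +0.54 to +0.61 |
| Gradual recovery | about -0.9 to -1.2 | +0.16 to +0.66 |
| Half persists | about -0.8 to -1.0 | -0.05 to -0.28 |
| Fully persists | about -1.0 to -1.3 | -0.64 to -1.14 |

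Across these courses the fitted baseline difference is about -0.7 to -1.3, against a truth of 0. With attrition the break-even fraction falls from 46% to as low as 34%.

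**Random slope added** (intraclass correlation 0.6, median progression 30 weeks). For full recovery the slope is +0.54 with a random-slope SD of 2 points/year and +0.29 with an SD of 4. For gradual recovery it turns negative, -0.15 and -0.67.

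**Chance that the favourable slope reaches two-sided p < 0.05** (full recovery, 374 per arm): 0.70 to above 0.99 with a random intercept; 0.43 and 0.09 with random-slope SDs of 2 and 4.

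**After the fix.** With categorical visit and treatment-by-visit terms, the end-of-radiotherapy contrast returns the assumed -2.0 and each later visit its own difference, under the same dropout assumption.

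**The case against.** The strongest case against the point is that the drop would not be hidden. SAP 11.3.3 tabulates means with standard errors and normal/impaired proportions by arm at each visit, including end of radiotherapy, and a reader could form a rough contrast from them. The analysis is exploratory and drives no confirmatory conclusion. Neurological harm is also captured elsewhere: adverse events of special interest are summarised by arm and by treatment period (SAP 12 and 12.1.3), and the self-reported QLQ-C30 cognitive scale is analysed separately during and after treatment (SAP 13.6.1). All of this stands and lowers the stakes. It does not supply an MMSE arm contrast with an interval at end of radiotherapy, and it does not make a straight line a suitable mean for this schedule.

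A reader might also infer that the model will turn cognitive harm into an apparent marizomib benefit. The documents do not support that as a general statement. Neither says that an MMSE deficit recovers, and marizomib is planned for up to 18 maintenance cycles, so a deficit may persist or grow. The break after radiotherapy and the dose reductions or skipped doses for CNS events (Protocol 5.5.1) make recovery possible, not established. Even where the slope favours marizomib, the fitted treatment term is negative, so the plot shows a lower marizomib line converging on control. The SAP does not say that the slope alone will be read.

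**Conclusion.** The point holds as a weakness of the specified model, of moderate weight because the analysis is exploratory and the per-visit descriptives are planned. Under an assumed 2-point deficit at end of radiotherapy, the model understates it by about one third to two thirds and creates a baseline difference that randomisation rules out in expectation. These two effects do not depend on recovery. The direction of the slope does: it favours marizomib at about +0.5 to +0.6 points/year if recovery is complete by the next visit (random intercept), less with a random slope, and goes against marizomib if the deficit persists.

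The drop size, SD, correlation, progression times, visit weeks and recovery shapes are assumptions. The random-intercept slope signs and break-even fractions do not depend on the drop size or SD; the significance probabilities do.

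**What to change.** In SAP 11.3.3, replace the linear time effect with visit as a categorical factor and treatment-by-visit terms. Use either a common baseline mean for both arms or baseline MMSE as a covariate. Pool sparse late visits under a rule stated in advance. Name the quantities to be interpreted: the arm difference with 95% CI at end of radiotherapy and at each 16-week visit. Plot the least-squares means from this model.

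The cost is SAP wording, a few more parameters and less precision at late visits. With seven visits and a common baseline mean there are 1 + 2 x 6 = 13 mean parameters instead of 4, and fewer after pooling. The change does not address informative dropout: MMSE stops at progression, and neither form of time solves that.
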